6.5 Criteria for Removal from Study

Patients will be removed from study when any of the criteria listed in section 3.2 or 6.4 applies. As above if patient develop progressive or new disease requiring additional systemic chemotherapy, they will be removed from study for further protocol directed assessments.

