3.2 Exclusion Criteria

Prior radiation to any part of the body including the lungs or thorax is not an exclusion criteria

- 3.2.1 Tumor edge is greater than 2 cm from the chest wall. The edge of tumor is the edge of the gross tumor volume or GTV as defined in radiation treatment planning software. This is determined by the treating radiation oncologist.
- 3.2.2 Tumors that are expected to require more than 10 fractions of radiation as determined by the treating radiation oncologist.
- 3.2.3 History of using bone anti-resorptive agents including bisphosphonates or RANK-L inhibitors within the last 1 year.
- 3.2.4 Inability to stand or sit upright for at least 30 minutes, which is necessary for ingestion of risedronate.
- 3.2.5 Hypocalcemia defined as serum total calcium lower than 8.5 mg/dL on most recent bloodwork that is within 3 months of administration of study drug/placebo
- 3.2.6 Severe renal impairment (EGFR <30 mL/min) on most recent bloodwork that is within 3 months of administration of study drug/placebo
- 3.2.7 Known allergy to risedronate or other bisphosphonates

- 3.2.8 Surgery affecting the bone or dental operations within the last 6 months

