6.0 Treatment Plan

6.1 Treatment Administration

Treatment will be administered on an outpatient basis.

Reported adverse events and potential risks of SBRT and risedronate are described in Section 8.

REGIMENT DESCRIPTION			
Agent	Dose	Route	Schedule
Risedronate	150 mg	Oral	Given once 7 – 21 days prior to initiation of SBRT
Matching Placebo	N/A	Oral	Given once 7 – 21 days prior to initiation of SBRT

Standard of care radiation therapy with SBRT will be given over the course of 3 – 10 fractions to a total dose of 50 – 60 Gy at the discretion of the treating radiation oncologist. Specific dose fractionations between 3 – 10 fractions and constraints will be at the discretion of the treating radiation oncologist and may be prescribed every day or every other day. Respecting the following constraints are encouraged but meeting these constraints is not required for inclusion in the study. In many cases meeting the rib constraint will not be possible.

Treatment planning will be performed utilizing a vac lock or body fix bag and optional abdominal compression at the discretion of the treating radiation oncologist. Planning CT chest may be performed with or without contrast at the discretion of the treating radiation oncologist. Utilization of motion management with 4D cinematic CT or a slow scan is required for determination of the internal target volume (ITV). Clinical treatment volume (CTV) creation is not necessary and is not our standard treatment paradigm with SBRT for peripheral lung tumors. The planning target volume (PTV) is generally created as a 0.5 cm expansion from the ITV, however the exact dimensions of this expansion are at the discretion of the treating radiation oncologist.

The following are encouraged but not required dose constraints.

Three Fractions

Serial Tissue	Volume	Volume Max (Gy)	Max Point Dose (Gy)	Endpoint (≥Grade 3)
Spinal Cord	<0.5 cc	18 Gy (6 Gy/fx)	22 Gy (7.33 Gy/fx)	myelitis
Cauda Equina	<5 cc	21.9 Gy (7.3 Gy/fx)	24 Gy (8 Gy/fx)	neuritis
Sacral Plexus	<3 cc	22.5 Gy (7.5 Gy/fx)	24 Gy (8 Gy/fx)	neuropathy
Esophagus*	<5 cc	21 Gy (7 Gy/fx)	27 Gy (9 Gy/fx)	stenosis/fistula
Ipsilateral Brachial Plexus	<3 cc	22.5 Gy (7.5 Gy/fx)	24 Gy (8 Gy/fx)	neuropathy
Heart/Pericardium	<15 cc	24 Gy (8 Gy/fx)	30 Gy (10 Gy/fx)	pericarditis
Great vessels	<10 cc	39 Gy (13 Gy/fx)	45 Gy (15 Gy/fx)	aneurysm
Trachea and	<4 cc	15 Gy (5 Gy/fx)	30 Gy (10 Gy/fx)	stenosis/fistula
Ipsilateral Bronchus*				

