9.2 Product Information for ACTONEL® (risedronate sodium) tablets

Product description: Risedronate is a pyridinyl bisphosphonate. The chemical name is [1-hydroxy-2-(3-pyridinyl)ethylidene]bis[phosphonic acid] monosodium salt. It has an affinity for bone hydroxyapatite and inhibits osteoclast mediated bone resorption.

Solution preparation:

Risedronate sodium is a fine, white to off-white, odorless, crystalline powder. It is soluble in water and in aqueous solutions, and essentially insoluble in common organic solvents. It is given orally in tablet form.

Dosage forms and ingredients:

The following information below was obtained from the product monograph from Allegran Pharma Co. Markham, Ontario L6G0B5 August 2017, Submission Control 205107

ACTONEL®

Medicinal Ingredients: Each risedronate sodium tablet for oral administration contains the equivalent of 5, 30, 35, or 150 mg of anhydrous risedronate sodium in the form of the hemipentahydrate with small amounts of monohydrate. **Nonmedicinal Ingredients** (Film-coated Tablets): Crospovidone, ferric oxide red (35 mg), ferric oxide yellow (5 and 35 mg), hydroxypropyl cellulose, hypromellose, indigo carmine (150 mg), lactose monohydrate (5, 30 and 35 mg), magnesium stearate, microcrystalline cellulose, polyethylene glycol, colloidal silicon dioxide and titanium dioxide.

Dosage Strength	Description	Packaging
5 mg	film-coated, oval-shaped, yellow tablets with "RSN" engraved on one face and "5 mg" engraved on the other	carton of 28 blister packaged tablets
30 mg	film-coated, oval-shaped, white tablets with "RSN" engraved on one face and "30 mg" engraved on the other	bottle of 30 tablets
35 mg	film-coated, oval-shaped, orange tablets with "RSN" engraved on one face and "35 mg" engraved on the other	carton of 4 blister packaged tablets
150 mg	film-coated, oval-shaped, blue tablets with "RSN" engraved on one face and "150 mg" engraved on the other	carton of 1 blister packaged tablet

Storage requirements and Stability:

All dosages are recommended for storage and are stable at controlled room temperature 20° to 25°C (68° to 77°F)

Route of administration:

Route of Administration	Dosage Form/Strength	Clinically Relevant Nonmedicinal Ingredients
oral	ACTONEL film-coated tablet 5 mg, 30 mg, 35 mg, and 150 mg	lactose monohydrate (5 mg, 30 mg and 35 mg)

Disposal:

There are no specific disposal recommendations for Actonel.

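### Section 6.5 turns the baseline exclusion list into continuing removal criteria, which invites inconsistent removal after randomisation, and section 11 has no rule to keep those patients in the analysis

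*Combined protocol and SAP*

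**What the plan says.** Section 6.5 opens with the rule "Patients will be removed from study when any of the criteria listed in section 3.2 or 6.4 applies". The first section it names is headed "3.2 Exclusion Criteria" and lists the conditions that bar entry to the trial. Two items matter here. Item 3.2.3 is "History of using bone anti-resorptive agents including bisphosphonates or RANK-L inhibitors within the last 1 year". Item 3.2.8 is "Surgery affecting the bone or dental operations within the last 6 months"; sub-items 3.2.8.1 and 3.2.8.2 narrow the dental part to work on the mandible. Neither item makes an exception for study drug, and neither is anchored to registration or dosing.

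Section 6.4, the other section named, withdraws patients whose progression or new cancer needs further chemotherapy, and keeps the data gathered before that withdrawal. Section 6.3 lists reasons for ending radiation early, including unacceptable adverse events. Section 6.5 does not cite it, although 6.4 speaks of patients taken off study for that reason. Section 11 defines no analysis population and does not say how patients removed after randomisation are handled.

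**The concern.** An exclusion criterion is normally applied once, before treatment. Section 6.5 makes the whole list operative during follow-up. Some items can become true only after randomisation, and some could do so because of the study drug or because of the bone damage the trial measures. Removal for such a reason is not random with respect to arm or outcome. If removed patients also drop out of the analysis, the comparison is no longer between the groups that were randomised. With 42 patients per arm and no dropout allowance stated in 11.4, there is little room for avoidable loss.

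**Working it through.** **1. The literal reading.** Three statements are set side by side:

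- Item 3.2.3 covers bisphosphonates taken in the past year.
- Section 9.2 says "Risedronate is a pyridinyl bisphosphonate".
- Section 6.1 schedules the dose as "Given once 7 – 21 days prior to initiation of SBRT".

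The latest primary scan after dosing is about 3 weeks (dose to SBRT) + 2 weeks (usual SBRT course, 6.3) + 13 weeks (3 months) + 8 weeks (calendar window) = 26 weeks. That is within one year. So at the primary assessment every dosed risedronate patient meets 3.2.3 through the study dose: 42 of 42 if all are dosed, against 0 of 42 on placebo for that trigger. Placebo patients can still meet 3.2 items in other ways. By an on-schedule 12-month visit the dose is at least 12 months and 7 days old, so this trigger has lapsed.

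**2. Whether that reading is intended.** Section 10 keeps the investigators blinded until all patients finish 12 months. Section 6.4 requires at least 3 months of follow-up, and the calendar in 6.6 has visits to 12 months. These cannot coexist with removing the whole active arm, so the literal reading is a defect of wording.

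**3. Which items can become true, and be noticed, after dosing.**

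- 3.2.3, a new anti-resorptive: yes. The calendar records bisphosphonate and RANK-ligand inhibitor use at 3, 6, 9 and 12 months. A fracture could plausibly prompt such treatment.
- 3.2.8, bone surgery or a mandibular operation: yes. Section 8.2 lists jaw osteonecrosis and loose teeth among the uncommon or rare risks of risedronate, so a link to arm is possible.
- 3.2.4, "Inability to stand or sit upright for at least 30 minutes, which is necessary for ingestion of risedronate": weak. The stated purpose is taking the tablet, which happens once.
- 3.2.5, "Hypocalcemia defined as serum total calcium lower than 8.5 mg/dL on most recent bloodwork that is within 3 months of administration of study drug/placebo": weak. It is tied to dosing, and the calendar schedules calcium only in the dosing column. The renal item, 3.2.6, has the same anchor.

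The links from fracture to treatment and from drug to dental work are inferences. Fracture and chest wall pain are not themselves items in 3.2.

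**4. Scale.** Inputs from 11.4: difference 0.22 − 0.11 = 0.11 mm, SD 0.20 mm, one-sided alpha 0.05, power 0.80. So d = 0.11/0.20 = 0.55.

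The plan's figure first: the normal approximation gives n = 2(1.645 + 0.842)²/0.55² = 12.37/0.3025 = 40.9, so 41 per arm. The two-sample t-test gives 41.57, so 42, which matches the plan.

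Power by t-test after equal, random loss in both arms (assumed rates; the documents give none):

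- no loss, 42 per arm: 0.804
- 5%, 40 per arm: 0.786
- 10%, 38 per arm: 0.767
- 20%, 34 per arm: 0.726
- 30%, 29 per arm: 0.664

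This is ordinary attrition arithmetic and does not measure bias. For bias, suppose a fraction f of one arm only is removed, and those patients differ from the rest of that arm by D in mean change. The observed arm mean then shifts by f × D. With D assumed to be one SD (0.20 mm), f = 0.05 gives 0.05 × 0.20 = 0.010 mm, or 9% of the 0.11 mm target. With f = 0.10 it gives 0.020 mm, or 18%. The direction depends on which arm loses patients.

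**The case against.** The strongest reply is that this is a slipped cross-reference that nobody would apply as written. Much of that stands, and four stronger readings that a reader might infer are not supported.

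- That the rule would empty the risedronate arm. Those running follow-up do not know the arm, and the schedule presumes that dosed patients stay. The 42-to-0 count shows that the wording is wrong; it is not a forecast.
- That low calcium or inability to stay upright would remove patients during follow-up. Both items are tied to dosing.
- That removal deletes the 3-month scan. Sections 2.0 and 5.0 say that the CTs are routine care and would be done whether or not the patient is enrolled, and 6.4 keeps data collected before withdrawal. The first post-dose calendar entry for anti-resorptive use is also the 3-month visit, alongside the primary CT. Loss is therefore more likely for the 6- to 12-month outcomes. It is still possible, because 6.5 ends protocol-directed assessments for patients removed for chemotherapy and does not say what happens to those removed under 3.2.
- That the pointer to 6.4 is also wrong. Section 6.4 does contain a withdrawal rule, and the next sentence of 6.5 restates it.

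What the reply does not answer is that 6.5 is the only section headed as removal criteria, that its wording is mandatory, and that 3.2.3 and 3.2.8 can be met visibly after dosing. Investigators who read it differently would remove different patients, and section 11 supplies no safeguard.

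**Conclusion.** The concern holds in a limited form. It is certain that 6.5 applies the exclusion list after randomisation and that, taken literally, it conflicts with the trial's own treatment and follow-up. The practical consequence is less certain: inconsistent removal for new anti-resorptive use, bone surgery or mandibular dental work, possibly related to arm or outcome. The documents give no rates, so no expected loss or bias can be stated. Under the assumptions shown, 5% to 10% loss costs about 2 to 4 points of power if random and equal, and shifts the effect by about 9% to 18% of its target if confined to one arm and to patients one SD apart. The primary endpoint is less exposed than the later fracture, pain and thickness outcomes. The correction is worth making because the rule decides who leaves the study and the remedy is almost free.

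**What to change.** Amend 6.5 and add a line to section 11:

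- Remove the reference to section 3.2 from 6.5. State that the 3.2 criteria determine eligibility up to study drug administration, at the time points that 3.2 and the calendar already give. Limiting them to registration would conflict with 3.2.5 and 3.2.6, which are anchored to dosing.
- State that patients who meet a 3.2 item after dosing, or are later found to have been ineligible, remain in follow-up for outcome data and are analysed in the arm to which they were randomised. Their routine CTs will exist anyway. Later anti-resorptive use is already recorded, so a supporting analysis that allows for it needs no new data.
- Reconcile 6.5 with 6.3, which it does not cite, and with 6.4, which it cites validly. Which criteria stop treatment is for the sponsor to decide.

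The cost is a few sentences in a protocol amendment, with no added visits, scans or patients.

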6.6 Study Calendar

	Baseline Prior to SBRT	Dosing (7- 21 days before SBRT)	During SBRT	1 month Post SBRT	3 ^f months post SBRT	6 ^f months Post SBRT	9 ^f months Post SBRT	12 ^f months Post SBRT
Informed consent	X							
Demographics Medical history History of diabetes Physical exam Performance status Vital signs Height, Weight, M ²		X						
Current Medications list	X				X			
Current or prior use of rank ligand inhibitors, bisphosphonates, and steroids with dates of use and dose as per Appendix G. ^h	X				X	X	X	X
CT chest with or without contrast	X ^a				X	X	X	X
Risedronate or placebo		X ^c						
Urine sample ^d	X				X	X	X	X
Serum Calcium EGFR Serum Creatinine Pregnancy test ^b		X						
Adverse event evaluation (Appendix E)					X			
Specific Radiation Related Chest wall Toxicity (Appendix K)				X ^e	X	X	X	X
Follow up phone call for assessment of adverse events without imaging (Appendix F)				X				
Fracture Incidence (Appendix Q)	X				X	X	X	X
Radiation Treatment Details (Appendix N)			X ^g					

^a Pre-SBRT CT chest scan will be the treatment planning scan. Fracture incidence will be assessed on CT scans

^b Urine pregnancy test (women of childbearing potential) performed within 1 week of treatment planning simulation for radiation.

^c Given once at 7 – 21 days prior to initiation of SBRT

^d For urine sample pick-up and transport, call [name] at [contact] (mobile), [contact] (office). If not available, call [name] at [contact] (mobile).

^e At the 30-Day time point this can be collected over the phone

^f Every 3 month follow-up, and CT imaging will have a window of +/- 8 wks

^g Appendix N may be completed during SBRT but should be completed within 12 weeks of completing SBRT

All pre-study activities must be completed within 12 weeks of the start of study drug including labs

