2.2 Secondary Objective(s)

- 2.2.1 In addition to the primary objective, we will further analyze the remaining routine follow-up chest CT scans, for mean cortical thickness change in regions of bone that received 0 – 10 Gy, >10 – 20 Gy, > 20 – 30 Gy, > 30 – 40 Gy, and > 40 Gy at all time points including 3 months, 6 months, 9 months, and 12 months. These scans are standard of care and would be performed regardless of inclusion on this trial. This will allow us to determine the potential persistence of effects from SBRT and bisphosphonate use.
- 2.2.2 We will assess and compare the incidence and grade (per modified CTCAE v.5) of radiation induced chest wall pain within the radiation treatment portal (within the 50% isodose line) at time of each routine follow up visit (3 months, 6 months, 9 months, and 12 months post SBRT). The purpose of utilizing a placebo and double-blind design is that chest wall pain is a subjective finding. Furthermore, it is unclear if chest wall pain from radiation is directly due to bone damage, nerve damage, muscle irritation, or a combination of all of these factors. The use of placebo will help us reduce the potential for bias in pain assessment.
- 2.2.3 We will assess and compare the incidence of rib and vertebral fractures (as noted on CT imaging) that occur within 12 months of irradiation and are within the radiation treatment field. The radiation treatment field will be defined as within the 50% isodose line.
- 2.2.4 The urine concentration of an osteoclast-specific biomarker, urinary N-telopeptide (NTX) indicating osteoclast activity will be assessed prior to SBRT and at each routine follow up visit (at 3 months, 6 months, 9 months, and 12 months post SBRT).

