2.3 Exploratory Objectives

- 2.3.1 We will analyze novel anatomic dosimetric substructures on already completed radiation plans such as rib neurovascular bundles. These anatomical structures will be contoured onto the stored planning CT scans and the raystation planning system will allow us to calculate the dose that these structures received. We will assess the relation between this calculated dose and development of/grade of chest wall pain during follow-up. The standard structure that is routinely contoured for these cases is a crude ring encompassing 2-3 cm of the entire chest wall. We are hypothesizing that dose to specific substructures in the chest wall may be more useful in the prediction of chest wall pain development.
- 2.3.2 If funding permits, we will analyze, and compare between groups, the urine concentration of markers of bone turnover activity. These will all be assessed prior to SBRT and at the 6 month follow up visit post SBRT.
- 2.3.3 We will analyze and compare between groups the urine concentrations of pain-associated cytokines prior to SBRT and at the 6 month follow up visit post SBRT. Also, if funding permits, the urine concentration of pain-related neurotrophic growth factors (proNGF, proBDNF, GDNF), and neuropeptides (CGRP and Substance P) will be measured.

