5.2 Secondary Outcomes

- 5.2.1 The change in mean C.Th of bones will be assessed in regions of bone that received 0 – 10 Gy, >10 – 20 Gy, > 20 – 30 Gy, > 30 – 40 Gy, and > 40 Gy at all time points including 3 months, 6 months, 9 months, and 12 months.
- 5.2.2 Chest wall pain incidence and grade will be collected as per modified CTCAE v. 5 within the within the 50% isodose line. Appendix K
- 5.2.3 Incidence of rib and vertebral fractures (as noted on CT imaging) that occur within 12 months of irradiation and are within the within 50% isodose line.
- 5.2.4 The urine concentration of an osteoclast-specific biomarker, urinary N-telopeptide (U-NTX) indicating osteoclastic activity will be assessed prior to SBRT and at each routine follow up visit (at 3 months, 6 months, 9 months, and 12 months post SBRT).

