5.3 Exploratory Outcomes

- 5.3.1 We will contour the neurovascular bundle that runs in the intercostal space for each patient within at least 3 cm of the planning tumor volume. We will then utilize stored treatment planning information and the raystation planning system to calculate the dose that this nerve bundle received at the time of treatment. As patients have already been assessed for development of chest wall pain at each follow up, we will assess for a dose response relationship between the dose to the nerve bundle and the subsequent development of and grade of any chest wall pain per the CTCAE v5.
- 5.3.2 Urine concentrations (pg/mL) of markers of bone turnover activity such as P1NP (procollagen type 1 pro-peptide), sclerostin, OPG (osteoprotegerin), TRAP5B, and pentosidine (an advanced glycation end-product (AGE)); will be analyzed using ELISAs. These markers will be assessed prior to SBRT and at the 6 month follow up visit post SBRT).
- 5.3.3 Urine concentrations (pg/mL) of pain-associated cytokines derived from the Isoplexis Codeplex Secretome Human Adaptive Immune and Innate Immune Chips which include GM-CSF, IL-1 β , IL-7, IL-17A, TNF- α , PDGF-BB, and VEGF will be assessed prior to SBRT and at the 6 month follow up visit post SBRT. In addition, other pro-inflammatory cytokines may be measured and analyzed on these chips as available. Also, if funding permits, the urine concentration (pg/mL) of pain-related neurotrophic growth factors (proNGF, proBDNF, GDNF) and neuropeptides (CGRP and Substance P) will be measured by ELISA.

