6.4 Duration of Follow-up

Follow-up for serious adverse events and mortality after the single dose of 150 mg of risedronate or placebo is administered will take place during the routine clinic visits during radiation treatment. Radiation treatments will occur within 1 – 3 weeks of taking the study drug. The 30 day follow-up window that is part of mandatory DSMC-SAE reporting will be considered 30 days from the end of all treatments of radiation. This visit can be either a phone call or a visit in person to review adverse events and may be conducted and documented in the medical record by either research study staff RNs or the treating physician. A window of +/- 7 business days is allowed for the 30 day followup assessment.

Specific toxicity related to radiation pneumonitis, radiation fibrosis, and chest wall pain will be collected at each followup point as per appendices K – M.

Patients removed from study for unacceptable adverse events will be followed until resolution or stabilization of the adverse event.

Patients will be followed for a minimum of 3 months for assessment of the primary objective.

Patients will be ideally followed in total for 12 months after completion of radiation therapy for the purposes of this study.

In the event that patients develop progressive disease or a new cancer, requiring additional chemotherapy they will be withdrawn from further study directed followup. In these situations, the followup schedules and imaging become dramatically different from what is directed on this protocol. Additionally further systemic chemotherapy treatments can heavily alter bone density/cortical thickness. As such, if patients develop new disease requiring additional systemic chemotherapy treatment outside of their initial SBRT, they will be withdrawn from study for further follow ups/study directed imaging. Any data that was collected prior to study withdrawal will still be used in analysis. **Immunotherapy or**

hormonal therapy for breast or prostate cancer will not be considered reasons for withdrawal.
Cryoablation or radiofrequency ablation will not be considered a reason for withdrawal from study.

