7.2 Incidence and Grade of Chest Wall Pain

Patients will be assessed at each routine follow up for development and or resolution of any chest wall pain/discomfort within the 50% isodose line. This will be graded per modified CTCAE v.5.

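### No chest wall pain grade is scheduled before SBRT, so newly developed pain has no graded reference; adding one is a cheap, optional improvement to a secondary comparison

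*Combined protocol and SAP*

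**What the plan says.** **Schedule.** In section 6.6 the row "Specific Radiation Related Chest wall Toxicity (Appendix K" has its first mark at 1 month. Footnote e ties that mark to the 30-day contact, so a shifted table column does not explain the empty earlier cells. The row "Fracture Incidence (Appendix Q" has a baseline mark, as do CT and urine. Section 6.4 says that "chest wall pain will be collected at each followup point as per appendices" K to M provide, and section 7.2 says "Patients will be assessed at each routine follow up for development and or resolution of any chest wall pain/discomfort within the 50% isodose line". Sections 2.2.2 and 11.2.2 name 3, 6, 9 and 12 months.

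**Outcome.** Objective 2.2.2 reads "We will assess and compare the incidence and grade (per modified CTCAE v.5) of radiation induced chest wall pain within the radiation treatment portal". Objective 2.3.1 adds "We will assess the relation between this calculated dose and development of/grade of chest wall pain during follow-up", and 5.3.1 refers to "the subsequent development of and grade of any chest wall pain per the CTCAE v5". Outcome 5.2.2 is neutral about onset: "Chest wall pain incidence and grade will be collected as per modified CTCAE v. 5". Section 11.2.2 is also neutral. It has no baseline term and no rule for pain already present.

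**Population.** Section 3.0 permits prior thoracic radiation, and section 3.2 does not exclude existing chest wall pain.

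**What exists before or around SBRT.** There is history and examination at the dosing visit and a baseline medication list (6.6). Analgesic use is recorded with reasons and dates (6.2), toxicity is evaluable from the time of the tablet (7.5), and there is an attribution scale (8.3).

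**The concern.** Most of the wording asks whether pain is new. Answering that needs a reference on the same scale, taken before the exposures of interest, and none is scheduled in the text reviewed. A patient who already has pain inside the later 50% isodose line could be counted as an event in either arm.

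Randomisation and blinding keep such cases balanced in expectation, so no bias towards one arm follows. The cost is dilution: the risk ratio moves towards 1. Two further analyses are not randomised comparisons and have no such protection: the correlation of grade 3 or higher pain with chest wall volume at 30 Gy or more (11.2.2), and the correlation of substructure dose with pain (11.3.1). Existing pain scored as an event adds noise to both.

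**Working it through.** **The plan's own figure.** Section 11.4 gives 42 per group for cortical thickness (difference 0.11 mm, SD 0.20 mm, one-sided 0.05, power 0.80). This reproduces: 41 per group by the normal approximation and 42 by the t-test (power 0.804). No sample size or power is stated for chest wall pain, and nothing below changes the 42.

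**Inputs for the illustration**
- n = 42 per arm, one-sided 0.05, no loss (from 11.4).
- New pain on placebo p = 0.35, the midpoint of the 30–40% in section 1.1. That figure is pain needing analgesics after SBRT; it is not stated to be new, and 7.2 covers any discomfort.
- Halved on risedronate, p = 0.175. This is an assumption, borrowed from the halving of bone loss in 11.4.
- b = prevalence of existing pain in the field; s = share of it scored as an event; k = rate of worsening by a grade relative to the new-pain rate, set at 0.5. The documents give none of these.

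**Formulas**
- With a baseline grade: risk = (1−b)p + bkp.
- Without one: risk = (1−b)p + b[s + (1−s)kp].
- Power = Φ(h√(n/2) − 1.645), with h = 2·arcsin√p₁ − 2·arcsin√p₂.

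**One case in full (b = 0.10)**
- With a baseline grade: placebo 0.9×0.35 + 0.1×0.5×0.35 = 0.3325; risedronate 0.9×0.175 + 0.1×0.5×0.175 = 0.1663. h = 0.389, and 0.389×4.583 − 1.645 = 0.138, so power is 0.555.
- Without, s = 0.5: placebo 0.315 + 0.1×(0.5 + 0.5×0.175) = 0.3738; risedronate 0.1575 + 0.1×(0.5 + 0.5×0.0875) = 0.2119. Power is 0.500.

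**Power across the range**

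| b | With baseline grade | s = 0.1 | s = 0.25 | s = 0.5 | s = 1 (worst case) |
|---|---|---|---|---|---|
| 10% | 0.555 | 0.543 | 0.526 | 0.500 | 0.457 |
| 20% | 0.530 | 0.505 | 0.473 | 0.429 | 0.369 |
| 30% | 0.505 | 0.468 | 0.422 | 0.367 | 0.302 |

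The gains over 10–30% are therefore about 0.01–0.04, 0.03–0.08, 0.06–0.14 and 0.10–0.20. The risk ratio is 0.50 with a baseline grade. Without one it is 0.57, 0.63 and 0.68 at s = 0.5, and 0.62, 0.71 and 0.78 at s = 1. With no existing pain, power is 0.58 either way.

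**Sensitivity**
- Worsening rate k from 0 to 1: the gain at s = 0.5 runs from 0.530 − 0.486 = 0.044 (k = 0, b = 10%) to 0.580 − 0.410 = 0.170 (k = 1, b = 30%).
- Smaller effect (risk ratio 0.67, b = 20%): 0.288 with a baseline grade, against 0.242 (s = 0.5) or 0.215 (s = 1).
- If the 35% already includes existing pain: new pain on placebo is (0.35 − b)/(1 − b), that is 0.278, 0.188 and 0.071 at b = 10%, 20% and 30%. Power with a baseline grade is then 0.46, 0.32 and 0.17. With everything scored and no baseline grade it is 0.355, 0.183 and 0.080. The worst-case gain is about 0.10, 0.14 and 0.09. Event counts are small at the last value, so the approximation is rough there.

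**The case against.** The strongest reply has four parts.

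1. **The forms cannot be seen.** Section 10.0 says chest wall pain is captured on Appendix K and a pre-filled adverse event log, and neither is in the text reviewed. A prior-pain or onset field would naturally sit there. This stands. A reader might infer that the trial never records earlier pain; the documents support only that no pre-SBRT grade is scheduled.

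2. **The wording and records already screen out old pain.** The objective is limited to radiation-induced pain, attribution runs down to unrelated (8.3), and history, examination and analgesic records exist. Toxicity is evaluable from the tablet (7.5). The 1-month grade precedes the usual onset at 3–8 months given in section 1.1. This stands in part. It makes the column in which all existing pain is scored a worst case, not the plan as written. But none of these is a grade before both tablet and SBRT: 7.5 starts at the tablet, and the 1-month grade follows both.

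3. **The 30–40% is total pain after SBRT.** Treating it as all new flatters the power available with a baseline grade. This stands, and the last sensitivity line shows how much.

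4. **A randomised, blinded comparison is valid without a baseline.** This stands. A reader might infer that the pain comparison is biased or invalid; nothing in the documents supports that.

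**Conclusion.** The gap holds as a gap in scheduling and event definition. Every place in the text reviewed that times chest wall pain grading puts it after SBRT, and 11.2.2 does not say how existing pain is handled.

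The consequence is loss of sensitivity in a secondary comparison and noise in the correlations. It is not a bias towards one arm, and the primary endpoint and sample size are untouched. The size cannot be derived from the documents. On the stated assumptions the gain in power runs from nil to about 0.20, and the upper end needs 30% prevalence with all of it scored. The effect on the correlations is not quantified.

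It would also be too much to infer that a baseline grade makes this comparison adequately powered: on these inputs power does not exceed 0.58. The point is an optional improvement, held with medium confidence because the two forms are unseen.

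**What to change.** 1. At the baseline or dosing visit, before the tablet is taken, record an Appendix K grade and the site of any chest wall pain. Section 8.2 lists bone and joint pain as a likely risedronate effect, so a grade taken after the tablet would not be a clean reference. Once the plan exists, classify the site as inside or outside the 50% isodose line.
2. In 11.2.2 define the event as new pain, or pain at least one grade above the baseline grade, and adjust the comparison of grades for baseline grade.
3. If Appendix K or the adverse event log already holds a prior-pain grade, only the calendar mark and the 11.2.2 wording are needed.

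**Cost.** One existing form at a visit that already has history and examination, one calendar mark, and a sentence or two in 11.2.2. A prospective baseline grade cannot be obtained after treatment, so patients already enrolled would need a grade abstracted from clinic notes or handled as missing. Patients with a high baseline grade have less room to worsen.
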